10.2.2. Bleeding Events and FVIII Usage

The number of bleeding events and quantity of FVIII replacement product used will be collected. At screening, the number of bleeding events and usage of FVIII replacement product will be documented for the past 12 months based on medical history and patient recollection. Bleeding events will be recorded by the patient as part of the patient diary. For each bleeding episode, the following parameters will be recorded: location (joint, muscle, internal organ vs other), type of bleed (spontaneous, traumatic, procedure-related), severity, and action taken/treatment.

Annualized bleeding rate will also be categorized by bleed location (joint, muscle, internal organ, other) and type of bleed (spontaneous, traumatic, procedure-related). Recombinant FVIII replacement therapy during the follow-up period will be recorded by the patient as part of the treatment diary. The following parameters will be recorded for each treatment event: reason for replacement therapy, name of product used, and dose.

10.3. Justification for Assessments

The clinical assessments and procedures used for the evaluation of efficacy and safety of SIG-001 are standard, widely used, and generally recognised as reliable, accurate, and relevant.

11. STUDY SPECIFIC COMMITTEES

11.1. Safety Review Committee (SRC)

A SRC composed of site Investigators, the Sponsor's representative and at least one independent individual with relevant experience in clinical research will be established. The SRC will review safety and efficacy on an ongoing basis. The SRC will review safety and efficacy parameters through at least the Week 8 visit for the first 3 patients enrolled in the study and at least the Week 4 visit for the remaining patients in any dose cohort, between dose cohorts, and for any cohort expansion. Additionally, the SRC will review all SAEs in an ongoing manner. The SRC may also meet on an ad hoc basis. Should a safety signal arise, the SRC will promptly convene for further assessment of subject safety. Notification of all SRC meetings and meeting outcomes will be sent to all participating sites. Additional information regarding membership and meeting frequency will be included in the *SRC Charter*.

12. SAFETY AND ADVERSE EVENTS

Throughout the course of the study, all AEs will be monitored and recorded in an AE section of the eCRF, including the AE's description, start and end date, seriousness, severity, action taken, and relationship to the Investigational Product. If AEs occur, the first concern will be the safety

PROTOCOL

Title: Safety and Efficacy of Encapsulated Allogeneic FVIII Cell Therapy in Haemophilia A
Study No. SIG-001-121

of the study patients. All AEs will be followed until resolved or stable and the outcome documented in the eCRF.

12.1. Definitions and Criteria

12.1.1. Adverse Events

Per ICH E2A, an AE is any untoward medical occurrence in a patient or clinical investigation subject administered a pharmaceutical product, not necessarily having a causal relationship with this product. An AE can therefore be any unfavourable or unintended sign, symptom, or disease temporally associated with the use of a medicinal product, whether or not related to the medicinal product.

Medical interventions such as surgeries, diagnostic procedures, and therapeutic procedures are not AEs in and of themselves. The medical condition requiring treatment should be captured as an AE/SAE as appropriate, while the action taken should be recorded as treatment of the AE.

12.1.2. Serious Adverse Events

A serious adverse event (SAE) or reaction is any untoward medical occurrence that at any dose:

- Results in death
- Is life-threatening
- Requires inpatient hospitalisation or prolongation of existing hospitalisation
- Results in persistent or significant disability or incapacity
- Is a congenital anomaly or birth defect
- Is an important medical event

The term “life-threatening” in the definition of “serious” refers to an event in which the patient was at immediate risk of death at the time of the event; it does not refer to an AE that hypothetically might have caused death if it were more severe.

Important medical events that may not result in death, be life-threatening, or require hospitalisation may be considered serious when, based upon appropriate medical judgment, they may jeopardise the patient or subject and may require medical or surgical intervention to prevent one of the outcomes listed in this definition. Examples of such medical events include allergic bronchospasm requiring intensive treatment in an emergency room or at home, blood dyscrasias or convulsions that do not result in inpatient hospitalization, or the development of drug dependency or drug abuse.

Medical and scientific judgment should be exercised in deciding whether expedited reporting is appropriate in other situations, such as important medical events that may not be immediately life-threatening or result in death or hospitalisation, but may jeopardise the patient or may require intervention to prevent one of the other outcomes listed in the definition above.

Seriousness (not severity) serves as a guide for defining regulatory reporting obligations. An event can be serious, but not necessarily severe (e.g., an event requiring overnight hospitalisation for a diagnostic procedure must be reported as an SAE even though the event may be mild in severity, or an event can meet the CTCAE definition of Grade 4 – life-threatening while not meeting the seriousness criterion of life-threatening potentially resulting in different reporting

PROTOCOL

Title: Safety and Efficacy of Encapsulated Allogeneic FVIII Cell Therapy in Haemophilia A
Study No. SIG-001-121

timelines). Furthermore, a severe AE is not necessarily serious (e.g., nausea of several hours' duration may be rated as severe, but may not be considered serious).

Pregnancy of a female partner of a study patient is not considered an SAE.

12.1.3. Unexpected Adverse Drug Reactions

An unexpected adverse drug reaction is a reaction for which the nature or severity is not consistent with the applicable product information (i.e. Investigator's Brochure, package insert for marketed products). Until product information is amended, expedited reporting is required for additional occurrences of the reaction. Reports that add significant information on specificity or severity of a known, already documented SAE constitute unexpected events. For example, an event more specific or more severe than described in the Investigator's Brochure would be considered "unexpected". Specific examples would be (a) acute renal failure as a labelled adverse drug reaction with a subsequent new report of interstitial nephritis and (b) hepatitis with a first report of fulminant hepatitis.

Guidance on reporting AEs and SAEs is described in Section 12.2.

12.1.4. Abnormal Laboratory Values

Any abnormality in a laboratory value that is new in onset or that has worsened in severity or frequency from the baseline condition and meets one of the following criteria will be recorded in the AE section of the eCRF:

- Requires therapeutic intervention
- Leads to patient withdrawal prior to administration of the Investigational Product
- Has accompanying or inducing symptoms or signs
- Is judged by the Investigator as clinically significant

12.1.5. Assessing Severity and Relationship

All AEs will be assessed on two descriptive parameters, severity and relationship to the Investigational Product.

- Severity refers to the intensity of an event and references impact on a patient's functioning.
- Relationship refers to the likelihood that the event being assessed was caused by the Investigational Product.

12.1.6. Severity

- All AEs or SAEs will be assessed by the Investigator for severity, according to CTCAE v5.0.
- The following general scale may be used with Investigator discretion to assign severity:
- When changes in the intensity of an AE occur more frequently than once a day, the maximum intensity for the experience should be noted. If the intensity category changes over a number of days, those changes should be recorded separately (with distinct onset dates).

PROTOCOL

Title: Safety and Efficacy of Encapsulated Allogeneic FVIII Cell Therapy in Haemophilia A
Study No. SIG-001-121

12.1.7. Relationship

Each AE will be assessed as to its relationship to the Investigational Product and its relationship to the laparoscopic procedure, based on the following criteria:

- Definitely Related: An AE, including laboratory test abnormality (if applicable), in which there is no uncertainty in its relationship
- Probably Related: There is strong medical evidence to suggest that the AE is related
- Possibly Related: There is medical evidence to suggest that there is a reasonable possibility that the AE may be related. However, other medical explanations cannot be excluded as a possible cause
- Unlikely Related: There is no medical evidence to suggest that the AE may be related, or there is another more probable medical explanation
- Not Related: The AE can be determined with certainty to have no relationship

All events assessed as unlikely related to the Investigational Product will be considered unrelated for the purpose of regulatory reporting. All events assessed as possibly or probably related to the Investigational Product will be considered related for the purpose of regulatory reporting.

The relationship assessment of possibly related will be used as the default assessment in the situation when the relationship assessment is omitted by the Investigator and until the relationship assessment is reported by the Investigator.

12.2. Reporting Procedures and Requirements

12.2.1. Adverse Events

Adverse events occurring from when the patient signs the ICF until the last study visit will be captured in the eCRF. Any medical conditions prior to the patient signing the ICF will be recorded in the medical history.

SAEs that occur in subjects that have signed the ICF, but are screen failures, will be captured in the Safety and Clinical databases.

The Investigator should report all AEs in the AE page(s) of the eCRF and source documents, regardless of seriousness, severity, and relationship. Whenever possible, an AE will be reported using a diagnostic term, (e.g., “common cold” or “upper respiratory infection” rather than “runny nose, cough, mild fever”) and should include the attributes described in Section 12.1.5.

12.2.2. Serious Adverse Events

Each AE will be assessed to determine whether it meets seriousness criteria (Section 12.1.2). Reports of SAEs require immediate reporting (within 24 hours of the site’s knowledge of the event) outlined below and to the IRB/IEC according to standard operating procedures whether or not the Investigator believes that the experience is related to the study product.

The SAE eCRF must be completed in the clinical database. The corresponding eCRFs requested on the SAE report must also be completed. Relevant medical records shall be provided at the time of the report. In the event that EDC is not accessible, the SAE must be reported by completing the paper SAE report form provided to the site. At a minimum, the initial report

PROTOCOL

Title: Safety and Efficacy of Encapsulated Allogeneic FVIII Cell Therapy in Haemophilia A
Study No. SIG-001-121

should include the following information:

- Event term
- Patient number and age
- Investigational Product
- Reporter's name and contact information

In the case of a “minimum report” (one that solely comprises the information bulleted above), a more detailed follow-up report should be sent as soon as more information becomes available, but no later than 7 calendar days after the date of the initial report. Each SAE should be followed up until resolution or stabilisation and for reported deaths, the Investigator should supply the Sponsor or its delegate and the IRB/IEC with any additional requested information (e.g., autopsy reports and terminal medical reports).

The Sponsor or its representative will be responsible for determining and in turn, reporting SAEs to regulatory authorities according to the applicable regulatory requirements.

Serious AEs that are ongoing at the last study visit should be followed until they resolve or the Investigator determines the event to be chronic (stabilized for at least 30 days), or until the subject is considered lost to follow-up.

Any SAE reported by the subject to the Investigator that occurs after the last assessment, and determined by the Investigator to be reasonably associated with the use of the study product, should be reported to the Sponsor.

Adverse events and concomitant medications terms will be coded using the Medical Dictionary for Regulatory Activities (MedDRA) and the World Health Organization Drug Dictionary Enhanced (WHO-DDE), respectively.

12.3. Safety and Risk Mitigation

The clinical safety of SIG-001 is further described in the *SIG-001 Investigator's Brochure*.

12.3.1. Mitigation of Exposure Risks

SIG-001 consists of genetically modified human cells (allogeneic cells) encapsulated in alginate hydrogel spheres. The alginate sphere component of SIG-001 is sufficiently porous to allow macromolecules, such as FVIII, to be secreted and pass into the surrounding space within the body, but not to allow allogenic cell components to pass. Once in circulation, FVIII secreted by SIG-001 spheres is expected to have distribution similar to that observed for other recombinant FVIII products (ReFacto, 2007; Xyntha, 2008). This is supported by circulating levels of FVIII observed in testing of SIG-001 in cynomolgus monkeys (*SIG-001 Investigator's Brochure* Section 4.2).

Direct exposure of patients to allogenic cells is expected to be extremely rare. First, there is an inability of ARPE-19 cells to exit SIG-001 spheres based on pore size. Second, in multiple nonclinical studies SIG-001 spheres demonstrated to have excellent integrity *in vivo*, with more than 92% spheres unbroken even after invasive extraction and necroscopic examination in animals. Third, *in vitro* stability data demonstrate that spheres do not degrade following 18 months of simulated aging at temperatures up to 50°C and 60°C, well in excess of temperatures

PROTOCOL

Title: Safety and Efficacy of Encapsulated Allogeneic FVIII Cell Therapy in Haemophilia A
Study No. SIG-001-121

encountered clinically. Fourth, vertebrates lack alginase, an enzyme necessary to break down alginic products. **CCI**

[REDACTED]

Thus, SIG-001 spheres are stable and sphere breakage *in vivo* has been demonstrated to be minimal. However, should any sphere breakage occur, ARPE-19 allogeneic cells are expected to be rapidly removed from the body by the immune system of the patient.

12.3.2. Mitigation of Contamination Risks

The SIG-001 shelf-life (96 hours) does not allow sufficient time for all microbiological contamination tests (lasting up to 14 days for bacteria and fungi and up to 35 days for mycoplasma) to be completed in full ahead of SIG-001 administration to a patient. However, multiple rapid microbial detection tests are completed prior to administration of SIG-001 to a patient (first stage certification criteria) and include negative results for gram stain, bacterial endotoxins and quantitative polymerase chain reaction (PCR) for mycoplasma, as well as no growth for 48 hours in the bacteria and fungi detection tests. Second stage certification criteria are completed after SIG-001 administration and include no growth for 14 days bacteria and fungi detection tests done via direct inoculation and no growth in the 35-day mycoplasma detection test. Both tests are read daily until completion. As such, there is a small risk that SIG-001 contamination may be identified after the laparoscopic administration is complete. In the unlikely event of detection of SIG-001 contamination after administration, the Sponsor will immediately notify the Investigator to ensure appropriate clinical management of the patient. Appropriate measures must be taken to ensure the safety and well-being of the patient. Such measures will be based on the sterility results (e.g. type of organism identified and antibiotic sensitivity), the patient health status/symptoms, and the Investigator's judgment. The clinical management of the patient may include additional visit(s) for physical examination, additional testing (e.g. complete blood counts, blood chemistry, inflammation markers such as C-reactive protein and blood cultures), and appropriate antibiotic treatment. A swab culture may be considered only if there is suspicion of inappropriate surgical site healing or presence of discharge from the surgical site. Investigators have the discretion to schedule additional visits and procedures as needed or decide to manage in-hospital. Surgical consultation and additional imaging, e.g. abdominal computed tomography (CT) with or without contrast may be needed to evaluate the patient progress and to inspect the abdominal cavity for fluid collections.

12.3.3. Potential Removal of SIG-001 Spheres

SIG-001 is intended to be permanently placed. In the event of unexpected serious safety issues related to SIG-001 that are not otherwise medically manageable (e.g. severe and persistent anaphylactic reaction), the Investigator may consider removal of the spheres. Preclinical data suggests that it is feasible to remove the majority of spheres after placement, which may require peritoneal lavage via laparoscopy or via laparotomy. Such procedures should be conducted at the discretion of the Investigator upon consultation with a surgery expert.

12.3.4. Mitigation of FVIII Inhibitor Development

New inhibitor formation in patients with haemophilia A and more than 150 exposure days to

PROTOCOL

Title: Safety and Efficacy of Encapsulated Allogeneic FVIII Cell Therapy in Haemophilia A
Study No. SIG-001-121

FVIII products is rare (Kempton, 2010). In addition, patients at higher risk of developing inhibitors such as those with current FVIII inhibitor titres > 0.6 NBU/mL or prior ITI are excluded from this study. Lastly, SIG-001 produces human FVIII with the same amino acid sequence of commercially available recombinant FVIII products that have a well-established safety profile (Mrooctocog alfa or BDDrFVIII; trade names ReFacto®, XYNTHA®), thus limiting the exposure of patients to neo-epitopes. As such, there is a small risk that SIG-001 administration may result in the development of FVIII inhibitors.

In the unlikely event of new development of FVIII inhibitors or persistently increased titres from baseline levels after SIG-001 administration, appropriate measures must be taken to ensure the safety and optimal care of the patient, including additional visit(s) for physical examination and frequent laboratory testing (including Bethesda assay for FVIII inhibitors). Clinical management will be instituted at the discretion of the Investigator and following established management guidelines (Carcao & Goudemand, 2018). Clinical management may range from monitoring alone to use of approved therapies to treat and prevent bleeds in patients with inhibitors, to institution of ITI. Should the Investigator consider that avoiding exposure to BDD-hFVIII produced by SIG-001 is necessary, removal of spheres may be considered (Section 12.3.3, Potential Removal of SIG-001 spheres).

12.3.5. Justification for Contraception Use

SIG-001 is locally administered, spheres (intact or broken) are not able to enter systemic circulation, and sphere components have been shown to be biocompatible, non-mutagenic, and non-genotoxic in nonclinical testing (*SIG-001 Investigator's Brochure* Section 4.3). This testing is conducted with consideration for ICH S2(R1) Guidance on Genotoxicity Testing and Data Interpretation for Pharmaceuticals Intended for Human Use, as well as relevant regional guidance/guidelines for advanced therapy medicinal products. Due to the nature of the product, exposure to systemic circulation or seminal fluid is not expected for the spheres or the cellular components. Therefore, the use of barrier methods (condoms) is considered to be an appropriate form of contraception for fertile males with partners that are women of childbearing potential, without further contraception requirements for partners of study participants. This determination is in accordance with US 21 CFR and EU Directive 2001/20/EC, and follows recommendations that condoms are sufficient contraception for non-genotoxic products made by the Clinical Trial Facilitation Group "Recommendations related to contraception and pregnancy testing in clinical trials" and recognized by, among other Agencies, the UK Medicines and Healthcare Products Regulatory Agency (MHRA) (Heads of Medicines Agency, 2014; MHRA, 2018). In the event that a pregnancy occurs in the female partner of a study subject, the Investigator will be required to obtain a Partner Pregnancy Consent Form in order to collect information regarding the outcome of the pregnancy. The Investigator will notify the trial Safety Officers immediately following pregnancy confirmation by completing and sending a Pregnancy Report Form.

13. STATISTICAL ANALYSIS

13.1. Statistical Considerations

No formal hypothesis testing is planned in the study. All analyses will be descriptive in nature.

PROTOCOL

Title: Safety and Efficacy of Encapsulated Allogeneic FVIII Cell Therapy in Haemophilia A
Study No. SIG-001-121

For each endpoint, detailed descriptions of the analyses will be provided in the *Statistical Analysis Plan* (SAP).

13.2. Determination of Sample Size

The sample size for this study is not based on statistical considerations, considering the limited number of available patients and the complexity of the study product. A maximum of 18 patients will be included in up to three dosing cohorts of a maximum size of six patients per cohort.

13.3. Conduct of Study Summaries

The number of patients who enrol, discontinue, or complete the study in each cohort will be summarized. Moreover, reasons for premature study withdrawal will be listed and summarized. Enrolment and major protocol deviations will be listed and evaluated for their potential effects on the interpretation of study results. The number of patients who reached the various stages of the study, how many dropped out and for what reasons will be described in the SAP.

13.4. Summaries of Demographic and Baseline Characteristics

Demographic and baseline characteristics (including age, sex, weight etc.) will be summarized using means, standard deviations, medians, and ranges for continuous variables and proportions for categorical variables, as appropriate. Summaries will be presented by dose cohort.

13.5. Efficacy Analysis

In general, efficacy analyses will be analysed by dose cohort and overall for the Efficacy Analysis Set, which will include all patients treated who have obtained at least one post-baseline efficacy assessment. The key efficacy analyses will include all data up to the end of Year 1 of follow-up. Additional analyses may be conducted including follow-up data in Years 2 to 5.

13.5.1. Development of FVIII Inhibitors

Testing for the development of FVIII inhibitors using the Nijmegen Bethesda inhibitor assay will be performed as described in the Schedule of Assessments (Table 2 Schedule of Assessments). The Nijmegen Bethesda inhibitor assay results will be summarized descriptively by visit as well as the number and proportion of patients with high titre values.

13.5.2. Factor VIII Activity Levels

Factor VIII activity (as measured by one-stage and chromogenic assays) will be summarized separately using summary statistics for each scheduled assessment, by dose cohort and overall. Factor VIII activity will be correlated to SIG-001 dose received.

13.5.3. Annualized Bleeding Rate (ABR)

The annualized number of bleeds per patient (annualized bleeding rate) will be calculated as the number of bleeding events divided by length of time on study product follow-up, in years. ABR will also be categorized by bleed location (joint, muscle, other) and type of bleed (spontaneous, traumatic, related to procedure).

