products; adequate FVIII levels will be ensured during hospital and home dosing. As needed, patients may be discharged with peripherally inserted central catheter (PICC) lines. Per the Investigator's discretion, patients may remain longer in the hospital for observation during FVIII administration.

Patients will be withdrawn from FVIII therapy after the Week 1 post-op visit at the Investigator's discretion. Throughout the study, all patients will be allowed access to on-demand FVIII to treat bleeding episodes, as perioperative management for surgery or other medical procedures, or as preventative treatment prior to vigorous physical activity.

Throughout the study, FVIII levels will be assessed at regular intervals. Per the Investigator's discretion, exogenous FVIII use will be washed out for a minimum of 96 hours (4 days for standard half-life FVIII products) and at least 168 hours (7 days for prolonged half-life rFVIII products) to ensure that only FVIII secreted by SIG-001 is measured.

ANALYTICAL METHODS:

Sample Size justification:

The sample size for this Phase 1/2 study is not based on statistical considerations.

Study Populations:

Efficacy Analysis Set includes all patients who received the study product and had at least one post-baseline efficacy assessment.

Safety Analysis Set includes all patients who received study product.

General Statistical Methods:

No formal hypothesis testing is planned in the study. Instead, results will be analysed using descriptive statistics. Data will be summarized by cohort and overall, where appropriate.

Absolute values and changes from baseline (Δ baseline) will be descriptively summarized for vital signs, laboratory data and FVIII inhibitor titres (Nijmegen Bethesda assay).

Data on FVIII activity, annualized bleeding and FVIII usage, as well as Haem-A-QoL, EQ-5D-5L questionnaires, joint health, and physical activity will be summarized descriptively and provided in subject listings. Questionnaires will be scored according to the recommendations from the questionnaire authors. Haem-A-QoL, EQ-5D-5L and HJHS scale scores and sub-scale scores and changes from baseline will be calculated at planned timepoints for each dose cohort and overall.

Full methods of analysis will be presented in the *Statistical Analysis Plan*.

Preliminary Efficacy Analysis:

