Annualized bleeding rates and FVIII usage can also inform preliminary efficacy of SIG-001. Patients with haemophilia A with FVIII activity below 2% suffer frequent spontaneous joint bleeds, but annualized spontaneous joint bleeds are close to zero once sustained FVIII activity rises above 12% (den Uijl et al., 2011). A significant reduction in exogenous FVIII usage is

PROTOCOL

Title: Safety and Efficacy of Encapsulated Allogeneic FVIII Cell Therapy in Haemophilia A
Study No. SIG-001-121

expected in patients reaching those FVIII levels. Therefore, data on bleeding rates and FVIII usage after SIG-001 administration will be assessed prospectively throughout the study.

Finally, exploratory endpoints include (1) change in health and quality-of-life as measured by the EQ-5D-5L and Haem-A-QoL instruments, respectively as well as (2) change in the number of target joints and frequency of bleeding episodes in target joints, as well as change in joint health scores as measured by the HJHS instrument. Low health-related quality-of-life is a long-recognized issue in haemophilia patients due to the physical, social, and emotional costs of the disease and the burden of lifelong treatment. It will be important to determine whether SIG-001 is able to impact this important facet of haemophilia patient care. In addition, poorly sustained FVIII levels often result in breakthrough bleeds and subsequent chronic joint disease. The effects of SIG-001 on health, quality-of-life and target joints and joint health will all be monitored as exploratory endpoints.

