7.3. Inclusion Criteria

Patients must meet all inclusion criteria to be eligible for participation in the study:

1. Males aged 18 years or older
2. Diagnosis of Haemophilia A as follows:
 - a) Severe ($< 1\%$ FVIII activity) receiving FVIII prophylaxis or on-demand treatment; or
 - b) Moderately-severe ($\geq 1\% - \leq 2\%$ FVIII activity) receiving FVIII prophylaxis
3. Greater than 150 exposure days to treatment with FVIII products
4. Fertile males (not surgically sterilized) who have sexual partners that are women of childbearing potential must be willing to use a barrier method of contraception (e.g. condoms) for at least 90 days post-SIG-001 administration
5. Normal levels of VWF antigen (≥ 50 IU/dL)

PROTOCOL

Title: Safety and Efficacy of Encapsulated Allogeneic FVIII Cell Therapy in Haemophilia A
Study No. SIG-001-121

6. Able and willing to provide informed consent
7. Willing to withdraw from FVIII prophylaxis during specified periods in the study

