7.5.2. Criteria for Re-Starting Prophylactic Therapy

Patients may restart prophylaxis if their FVIII level is <2% normal activity in two separate occasions done at least one week apart after 8 weeks following SIG-001 placement. If a patient needs to restart prophylaxis prior to Week 8, the Investigator should contact the Medical Monitor for approval.

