7.5.3. Prohibited Medications and Therapies

Medications that increase the risk of bleeding or that are contraindicated for laparoscopic surgery per the site's standard of care will be prohibited. Examples may include use of aspirin or nonsteroidal anti-inflammatory drugs (NSAIDs) in the 5 days period prior to, and following SIG-001 administration.

Emicizumab is prohibited any time during the trial unless the patient has already met the criteria to restart prophylaxis.

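### Section 13.5.3 keeps counting follow-up after prophylaxis or emicizumab is taken up, so the annualised bleeding rate understates bleeding under SIG-001 alone

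*Protocol*

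**What the plan says.** Section 13.5.3 gives a formula: the ABR "will be calculated as the number of bleeding events divided by length of time on study product follow-up, in years". Its only breakdowns are by where the bleed was and what kind of bleed it was. Section 13.5 takes everything to the end of Year 1 for the key efficacy analyses, with further analyses using Years 2 to 5.

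Nothing closes the denominator when other treatment begins. The implant is meant to be permanent (12.3.3), and treated patients stay in the trial (6.6.1) unless they withdraw or the investigator removes them (7.6). Section 7.5.2 says "Patients may restart prophylaxis if their FVIII level is <2% normal activity in two separate occasions done at least one week apart", counted after Week 8; an earlier restart needs the Medical Monitor's approval. Section 7.5.3 adds: "Emicizumab is prohibited any time during the trial unless the patient has already met the criteria to restart prophylaxis". Neither event ends follow-up or the bleed count.

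On what bleeding to expect, 6.5.2 says "Patients with haemophilia A with FVIII activity below 2% suffer frequent spontaneous joint bleeds" and presents ABR as information on the preliminary efficacy of SIG-001. Under 7.3, severe patients may enter "receiving FVIII prophylaxis or on-demand treatment"; moderately severe patients must be on prophylaxis. Prior bleeding "will be documented for the past 12 months based on medical history and patient recollection" (10.2.2).

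**The concern.** Restart follows product failure, since the stated trigger is two FVIII values below 2%. From then on, any bleeds prevented by prophylaxis or emicizumab lower a rate that is meant to describe SIG-001. The earlier the implant fails, the more of the denominator belongs to the other treatment, so the worst failures are diluted most. In cohorts of at most six patients this can also blur the comparison between doses.

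There is no control arm, so the ABR will be read either alone or against the prior 12 months. What the reader sees then depends on the baseline regimen:

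- A severe patient treated on demand before the study, who takes up prophylaxis or emicizumab after failure, can show a large fall in ABR with no product effect.
- A patient on prophylaxis at baseline shows a worsening that is smaller than the one he had while uncovered.

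A switch to emicizumab is the hardest case to see. Section 13.5.4 counts uses of FVIII replacement products only, so both FVIII use and ABR can be low in a patient whose implant has failed.

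**Working it through.** The protocol states no expected ABR and no power calculation, so there is no planned figure to reproduce. The check is direct rate arithmetic.

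**Inputs from the protocol.** Horizon T is 52 weeks (key analysis, 13.5) or 260 weeks (last scheduled visit, Table 2). Restart is possible after Week 8 on two low values (7.5.2). Table 2 has FVIII samples at Weeks 8, 10, 12, 16, 20 and 24, so Week 10 is an early restart. It becomes about Week 12 if both scheduled samples must fall after Week 8.

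**Assumptions, not in the protocol.** No product effect; uncovered rate L0 = 20 bleeds a year (range 10 to 30); covered rate L1 = 2 a year (range 1 to 5).

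**Formula.** With restart at week r:

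- ABR under 13.5.3 = [L0 × r + L1 × (T − r)] / T
- Fraction by which it falls short of L0 = (1 − r/T) × (1 − L1/L0)

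The shortfall is positive whenever L1 is below L0 and zero when they are equal.

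| Restart | T | ABR at L0 = 20, L1 = 2 | Too low by | Range over the assumed rates |
|---|---|---|---|---|
| Week 10 | 52 | (200 + 84)/52 = 5.46 | 73% | 40–78% |
| Week 12 | 52 | (240 + 80)/52 = 6.15 | 69% | 38–74% |
| Week 24 | 52 | (480 + 56)/52 = 10.31 | 48% | 27–52% |
| Week 36 | 52 | (720 + 32)/52 = 14.46 | 28% | 15–30% |
| Week 10 | 260 | (200 + 500)/260 = 2.69 | 87% | 48–93% |

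The ends of each range come from L1/L0 = 5/10 and 1/30. At Week 10, for example, (42/52) × 0.5 = 40% and (42/52) × (29/30) = 78%. Treating Week 1 as covered by perioperative FVIII changes the Year-1 values for Weeks 10, 24 and 36 to 5.12, 9.96 and 14.12, which adds 1 to 2 percentage points.

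**Read against baseline, restart at Week 10.**

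- On demand at baseline (20 a year): 5.46/20 = 0.27, a 73% fall with no product effect.
- Prophylaxis at baseline (2 a year): 5.46/2 = 2.73 times baseline at Year 1 (range 1.19 to 6.58) and 2.69/2 = 1.35 times over 5 years (1.04 to 2.12). The true ratio while uncovered is 20/2 = 10 (2 to 30).

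**Cohort illustration.** Six patients; three restart at Week 12 with the rates above, and three stay at 2 a year. The Year-1 mean under 13.5.3 is (3 × 6.15 + 3 × 2)/6 = 4.1. The mean of the rates before restart is (3 × 20 + 3 × 2)/6 = 11.0.

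**Does FVIII use expose the failure?** Take one infusion per bleed before a Week 10 restart.

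- Prophylaxis at 1 to 3 infusions a week (the frequency in 3.2) gives (200 + 52 × 42)/52 = 45.8 to (200 + 156 × 42)/52 = 129.8 uses a year, which does expose it.
- Emicizumab with 2 FVIII uses a year gives (200 + 84)/52 = 5.5, which does not.

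**The case against.** **The SAP may deal with it.** Section 13.1 defers detail to the SAP, and a split there would not be forbidden. But the numerator and denominator are stated in 13.5.3, not deferred. A SAP that split at restart would be supplementing or departing from a definition the protocol already gives.

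**ABR over all follow-up is legitimate.** The secondary objective concerns bleeding after SIG-001 administration, and counting all bleeds over all follow-up answers that as a treatment-policy summary. This stands, and it is why that ABR should be kept. It does not describe the product alone, and the protocol does not say which reading is meant.

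**Other outputs show the failures.** ABR and FVIII data "will be summarized descriptively and provided in subject listings", and 13.5.2 summarises FVIII activity at each scheduled assessment, so the low values behind a restart will be visible before an emicizumab switch. This stands too, and lowers the risk of serious misreading. It does not correct the ABR summary by cohort.

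**The false-benefit case is conditional.** Section 7.5.2 speaks of restarting, and an on-demand patient has no prophylaxis to restart; the protocol does not say such patients will begin it. Nor does it plan a change-from-baseline ABR; 10.2.2 only collects the history. For patients on prophylaxis at baseline, the assumed rates never produce an apparent benefit. All this is right, so the on-demand result is only what can happen.

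**Lower bleeding on cover is inferred.** Section 6.5.2 contrasts activity below 2% with sustained activity above 12%, and 3.2 notes that breakthrough bleeds occur on replacement therapy. The bias exists only if cover lowers bleeding. In addition, restart is optional, and 13.5 says the later-year analyses may be done where the synopsis says they will be.

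**Stopping at restart is informative and noisy.** Restart depends on failure, and early failures supply little time. This is a real cost and limits how the new rate can be summarised.

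**Conclusion.** The concern holds. As written, 13.5.3 mixes time on SIG-001 alone with time on prophylaxis or emicizumab, and so understates bleeding under SIG-001 alone whenever that cover lowers bleeding. The direction is firm under that condition. The size is not, because both bleed rates and the restart weeks are assumed: roughly 40% to 78% too low at Year 1 for a Week 10 restart, 15% to 30% for Week 36, and 48% to 93% for a Week 10 restart if the rate is accumulated over 5 years.

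This should be fixed, but it does not threaten the trial. ABR is a secondary, descriptive endpoint. Dose escalation uses safety and FVIII activity (6.4) and is not affected.

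**What to change.** Amend 13.5.3 to add the following, with matching SAP tables:

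- **Uncovered ABR, per patient.** Time at risk starts when perioperative or continued FVIII cover ends. It stops at the earliest of first restart of prophylaxis (FVIII or emicizumab), end of the analysis period, or withdrawal or removal. The on-demand, perioperative and pre-activity doses allowed by 7.5.1 do not stop it.
- **Never uncovered.** Patients who do not come off FVIII after Week 1 contribute no uncovered time and are counted and listed separately.
- **Covered ABR.** Report it separately, with the number restarting and the time to restart.
- **Individual display.** Show each patient's values with time at risk, the baseline 12-month rate and the baseline regimen.
- **All-follow-up ABR.** Keep it alongside as the summary of overall experience.

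In 13.5.4, leave total FVIII use as defined and flag patients on emicizumab, so that low use is not read as a SIG-001 effect. No clinical restart rule changes.

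No new data are needed. Section 10.2.2 records "reason for replacement therapy, name of product used, and dose" for each treatment. Sections 7.5.1 and 9.2.4 record why FVIII was continued after Week 1, and 7.5 captures added medications.

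The price is noise. With 9 uncovered weeks (Week 1 to Week 10), one bleed annualises to 52/9 = 5.8. At a true 20 a year, the Poisson standard deviation of one patient's ABR is √(20 × 9/52) × 52/9 ≈ 11. Individual values with time at risk and the all-follow-up ABR must therefore stand beside any cohort figure.
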